7.1.2 Physical Examination

At screening or Day 0 visit, a targeted physical exam will be performed based on participant's clinical history and height and weight will be collected. Vital signs (temperature, heart rate, respiration and blood pressure) will be collected at screening and prior to each vaccination. The exam will be performed by qualified study personnel to assess general physical condition and will include the following areas/systems: supraclavicular and axillary lymph nodes, cardiovascular, pulmonary, abdomen, skin.

At visits following the first vaccination a targeted physical examination may be conducted based on interim medical history.

7.1.3 Reactogenicity Assessments

Will include brief history for assessment of AE/SAEs just prior to and following vaccination, which includes an assessment of pain, tenderness, erythema, induration and warmth at the injection site; fever, chills, arthralgia/joint pain, malaise/fatigue, myalgia/body aches, headache, nausea, vomiting and abdominal pain.

The vaccination site will be examined at the end of the 15-minute observation period following each vaccination on Day 1 and Day 29 if applicable as well as all other timepoints if indicated.

7.1.4 Memory aids

Following each vaccination, all participants will complete a participant memory aid for 8 days (Days 1-8 [all participants] and Days 29-36 [participants in the vaccine naïve cohort only]).

Following each vaccination, and if applicable at Day 8 visits, memory aids will be reviewed with the participant. The study staff objective assessment of the reactogenicity will be documented. Memory aids are not source documents and will be used as a tool for the study team to interview the participants about their reactogenicity. The study team will fill up the source, based on the memory aid and the source is captured in the database. The memory aids themselves will be destroyed.

7.2 Concomitant Medications/Treatments

7.2.1 General

All ongoing medications and therapies at screening will be considered prior medications.

Concomitant medications will include all current medications and medications taken within the 30 days prior to enrollment (prescription and over-the-counter drugs, vitamins and supplements, topical products, and vaccinations) through 34 days after the second vaccination (approximately Day 57-60 for participants who receive both doses of vaccine or early termination (if prior to Day 60), whichever occurs first. Assessment of eligibility also will include a review of permitted and prohibited medications (per the exclusion criteria).

Administration of any concomitant medications, therapies or vaccines will be documented in the participant's medical record and eCRF.

Contraceptive status is assessed and documented at every scheduled clinic visit for participants who were born female and who are sexually active in a way that could lead them to becoming pregnant. Prior to enrollment and throughout the study, staff will ask participants to verbally confirm their use of effective contraceptive methods.

7.2.2 For Hematologic Malignancies Cohorts:

7.2.2.1 Supportive Care

- Supportive care measures including blood products, infection prophylaxis and growth factors will be administered according to institutional guidelines.

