5.2 Exclusion Criteria

All participants meeting any of the exclusion criteria at baseline will be excluded from study participation.

- 5.2.1 Within 14 days of known exposure to someone with confirmed SARS CoV2 infection or COVID-19.
- 5.2.2 Acutely ill or febrile 24 hours prior to or at the Screening Visit (Day 0). Fever is defined as a body temperature $\geq 38.0^{\circ}\text{C}/100.4^{\circ}\text{F}$. Participants meeting this criterion may be rescheduled within the relevant window periods. Afebrile participants with minor illnesses can be enrolled at the discretion of the investigator.
- 5.2.3 Participants on the vaccine naïve arms cannot have received any doses of the COVID-19 vaccine.

Participants who have not completed a standard vaccination series due to initiation of vaccination in a foreign location (e.g., single dose of Astra-Zeneca vaccine or a similar situation) may be enrolled after discussion with the principal investigator.

Participants on the booster arms must have received all doses of their initial COVID-19 vaccine (Participants vaccinated with the Janssen vaccine must have received the single dose of that EUA vaccine for COVID19, but all others must have received 2 doses) at least 4 weeks prior to vaccination on protocol. Participants will be allowed to enroll if they have already received booster doses of vaccine prior to enrolling on the protocol at least four weeks prior to vaccination on protocol. In this case, the protocol will administer a single booster dose of vaccination. Documentation will be required.

- 5.2.4 Known diagnosis of chronic pulmonary disease (e.g., chronic obstructive pulmonary disease, asthma) that is not controlled.
- 5.2.5 Chronic cardiovascular disease that is not controlled.
- 5.2.6 Participants with a history of myocarditis (inflammation of the heart) or pericarditis (inflammation of the pericardium)
- 5.2.7 History of anaphylaxis, urticaria, or other significant adverse reaction requiring medical intervention after receipt of a vaccine.
- 5.2.8 Bleeding disorder considered a contraindication to intramuscular (IM) injection or phlebotomy.
- 5.2.9 Participated in an interventional clinical trial with an investigational agent within 28 days prior to the Screening Visit (Day 0) or plans to do so while participating in this study. The site investigator may enroll a participant on the trial earlier than 28 days if enough time has passed to ensure that at least five half-lives have occurred.

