- 5.2.10 Prior/Concomitant Therapy
 - Has received prior radiotherapy within 14 days before the first dose of study treatment. Participants must have recovered from all radiation-related toxicities, not require corticosteroids, and not have had radiation pneumonitis. A 7-day washout is permitted for palliative radiation (\leq 2 weeks of radiotherapy) to non-central nervous system (CNS) disease.
 - Has received a live vaccine within 30 days before the first dose of study treatment. Examples of live vaccines include, but are not limited to, the following: measles, mumps, rubella, varicella/zoster (chicken pox), yellow fever, rabies, Bacillus Calmette–Guérin (BCG), and typhoid vaccine. Seasonal influenza vaccines for injection are generally killed virus vaccines and are allowed; however, intranasal influenza vaccines (e.g., FluMist®) are live attenuated vaccines and are not allowed.
- 5.2.11 Has received an inactivated vaccine within 14 days before the first dose of study treatment.
- 5.2.12 Have major surgical procedures within 28 days or non-study-related minor procedures within 7 days before the first dose of study treatment. In all cases, the participant must be sufficiently recovered and stable before treatment administration.
- 5.2.13 History of severe allergic reactions to any components of the study treatment.
- 5.2.14 Has uncontrolled intercurrent illness, including but not limited to, ongoing or active infection, symptomatic congestive heart failure, uncontrolled hypertension, unstable angina pectoris, cardiac arrhythmia, severe or ongoing interstitial lung disease (ILD), serious chronic gastrointestinal conditions associated with diarrhea, or psychiatric illness/social situations that would limit compliance with study requirement, substantially increase risk of incurring AEs, or compromise the ability of the participant to give written informed consent.

- 5.2.15 Active tuberculosis (clinical evaluation that includes clinical history, physical examination and radiographic findings, and tuberculosis testing in line with local practice).
- 5.2.16 History of (non-infectious) pneumonitis that required steroids or has current pneumonitis.
- 5.2.17 Has involvement in the planning and/or conduct of the study.
- 5.2.18 Female who is pregnant or breastfeeding
- 5.2.19 Male or female participant of reproductive potential who are not willing to employ effective birth control from screening to 30 days after the last dose of study treatment.

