7.2.2.2 Concomitant Medications

Recommendations with regard to specific types of concomitant therapies, supportive care; diet and other interventions are as follows:

- Concomitant medications are recommended as prophylaxis for nausea, vomiting, and infections, and are recommended according to institutional standards. Myelosuppression is expected in participants with acute leukemia, lymphoma or myeloma, or post-stem cell transplantation due to underlying disease, as well as due to chemotherapy, or both. Many participants may have neutropenia, thrombocytopenia, or both at study entry.
- Significant or life-threatening myelosuppression may be managed with growth factor support and blood transfusion according to institutional standard of care, American Society of Clinical Oncology (ASCO) Practice Guidelines, and/or NCCN Practice Guidelines.
- Infections secondary to myelosuppression are common in participants with hematologic malignancies, and may be related to underlying disease, chemotherapy, or both. Therefore, the use of prophylactic antibiotics, antifungal agents, and antiviral agents is recommended according to institutional standards.
- If a prohibited medication is considered essential for the participant well-being, continuation on study with concomitant administration of such medication(s) will need to be discussed with and approved by the principal investigator.

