11.4.1.2 Per-Protocol Set

The Per-Protocol (PP) Set consists of all FAS participants who meet all of the following criteria:

- Complied with the injection schedule.

- Complied with the timings of immunogenicity blood sampling to have post-injection results available for at least one assay component corresponding to the immunogenicity analysis objective.
- Have had no major protocol deviations that impact immune response during the period corresponding to the immunogenicity analysis objective.

The PP Set will serve as the primary set for the analysis of immunogenicity data in this study.

11.4.1.3 **Solicited Safety Set**

The Solicited Safety Set consists of all participants who received at least one study injection, and contribute any solicited AR data; i.e., have at least one post-baseline solicited safety assessment. The Solicited Safety Set will be used for the analyses of solicited ARs.

11.4.1.4 **Safety Set**

The Safety Set consists of all participants who received at least one study injection. The Safety Set will be used for analysis of safety except for the solicited ARs.

11.4.2 **Statistical Analyses**

11.4.2.1 **Immunogenicity Analyses**

The analyses of immunogenicity will be based on the PP Set. If the number of participants in the FAS and PP Set differ (defined as the difference divided by the total number of participants in the PP Set) by more than 10%, supportive analyses of immunogenicity may be conducted using the FAS.

For the primary immunogenicity endpoint, geometric mean titer (GMT) of specific bAb with corresponding 95% CI at each timepoint and geometric mean fold rise (GMFR) of specific bAb with corresponding 95% CI at each post-baseline timepoint over pre-injection baseline at Day 1 will be provided. Descriptive summary statistics including median, minimum, and maximum will also be provided.

For the secondary immunogenicity endpoint, GMT of specific nAb with corresponding 95% CI at each timepoint and GMFR of specific nAb with corresponding 95% CI at each post-baseline timepoint over pre-injection baseline at Day 1 will be provided. Descriptive summary statistics including median, minimum, and maximum will also be provided. For summarizations of GMT values, antibody values reported as below the LLOQ will be replaced by $0.5 \times \text{LLOQ}$. Values that are greater than the upper limit of quantification (ULOQ) will be converted to the ULOQ.

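### Antibody received as treatment is not excluded, flagged or recorded through the last sample, so the plan can credit it to the vaccine; the direction and size of the bias are unknown

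*Combined protocol and SAP*

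**What the plan says.** **Permission.** Section 7.2.2.1, for the hematologic cohorts, reads: "Supportive care measures including blood products, infection prophylaxis and growth factors will be administered according to institutional guidelines". Section 7.2.2.2 adds that significant myelosuppression may be managed with "growth factor support and blood transfusion according to institutional standard of care".

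**Exclusions.** The prior-therapy and vaccine criteria (5.2.10 and 5.2.11) cover radiotherapy, live vaccines (a participant who "Has received a live vaccine within 30 days before the first dose of study treatment") and inactivated vaccines. Criterion 5.2.9 excludes anyone who "Participated in an interventional clinical trial with an investigational agent within 28 days prior to the Screening Visit", with a five-half-lives exception, and also bars plans to join such a trial during the study. Section 7.2.1 identifies prohibited medications by reference to the exclusion criteria, and none of them concerns antibody-containing products given as care.

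**Analysis set.** Section 11.4.1.2: "The PP Set will serve as the primary set for the analysis of immunogenicity data in this study". Beyond compliance with injections and sampling, its remaining criterion is: "Have had no major protocol deviations that impact immune response during the period corresponding to the immunogenicity analysis objective".

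**Analysis.** Section 11.4.2.1 gives GMT and GMFR for bAb (primary) and nAb (secondary), with GMFR referred to Day 1. For nAb it adds the percentage with seroconversion, which the endpoint's label attributes to vaccination.

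**Recording.** Section 7.2.1 says "Administration of any concomitant medications, therapies or vaccines will be documented" in the medical record and eCRF, but the window that defines concomitant medication runs "through 34 days after the second vaccination".

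**The concern.** Immunoglobulin, plasma and anti-SARS-CoV-2 antibodies can carry antibody that the study assays may measure. If a participant receives one, part of the measured titer comes from the product. Each cohort is analysed without a concurrent control, so no comparison removes that part.

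The analysis by hematologic versus solid tumor (Section 11.4.2.5) is exposed as well. The written permission applies only to the hematologic cohorts, so exposure may differ between the two groups. The protocol itself describes prolonged B-cell depletion and infection risk after CAR T therapy (2.4.4) and high infection-related risk in CLL (2.4.5). In these groups the measured response is of most interest and may be hardest to attribute.

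**Working it through.** The plan states no power or sample-size calculation (11.1 sets out estimation only), so there is no figure to reproduce. The check reads the rules in sequence and then illustrates size on stated assumptions.

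**1. Does any rule remove an affected sample?**
- Eligibility: no. Criterion 5.2.9 reaches only agents from other trials.
- Per-Protocol Set: no. A permitted treatment is neither non-compliance nor, as written, a deviation.
- Full Analysis Set (11.4.1.1): no. The optional supportive analysis would keep the same samples.
- Nucleocapsid assay (7.3.2): no. It serves baseline status and infection, no analysis rule is tied to it, and a spike-only antibody would not register on it.

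**2. Could exposure be identified afterwards?**
- *Vaccine-naïve cohorts.* Thirty-four days after a Day 29 dose is Day 63; Section 7.2.1 itself puts the end at about Day 57–60. Antibody is an endpoint at Days 209 and 394 (Section 3.2). Even from Day 63, that leaves 209 − 63 = 146 and 394 − 63 = 331 days without a defined recording window.
- *Booster cohorts.* The window is tied to a second vaccination, which these participants do not receive by default. Appendix G marks concomitant medications at screening only. Section 6.1.3.1 adds a review at Day 1. The later visit lists, through Day 360, include none.

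**3. Direction.**
- *Product started or increased after Day 1.* Baseline is unaffected and the later titer is raised, so GMT, GMFR and seroconversion all move up.
- *Product present at Day 1.* Baseline is raised. Assume a passive titer of 8 × LLOQ that persists, a vaccine-induced titer of 8 × LLOQ, and additivity. Without the product the fold rise is 8/0.5 = 16 and the participant seroconverts from an undetectable baseline. With it, the fold rise is (8 + 8)/8 = 2, below the required 4, so a true responder is missed. GMT is still inflated.

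**4. Size, upward case only.** The number of recipients and the passive titers are assumptions. Intervals are Clopper–Pearson 95%. True seroconversion is assumed to be 20%.

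| Passively positive non-responders | n = 20 | n = 30 |
|---|---|---|
| 0 | 4/20 = 20% (5.7–43.7) | 6/30 = 20% (7.7–38.6) |
| 1 | 25% (8.7–49.1) | 23.3% (9.9–42.3) |
| 2 | 30% (11.9–54.3) | 26.7% (12.3–45.9) |
| 4 | 40% (19.1–63.9) | 33.3% (17.3–52.8) |

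Each adds 1/20 = 5 points at n = 20, or 1/30 = 3.3 points at n = 30.

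For GMT, a value at F × LLOQ replaces the imputed 0.5 × LLOQ in k of n participants, so the multiplier is (F/0.5)^(k/n) = (2F)^(k/n). At n = 20:

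| F | k = 1 | k = 2 |
|---|---|---|
| 4 | 1.11 | 1.23 |
| 8 | 1.15 | 1.32 |
| 32 | 1.23 | 1.52 |
| 100 | 1.30 | 1.70 |
| 1000 | 1.46 | 2.14 |

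**5. Does excluding affected samples solve it?** Not alone. Take 4 true seroconverters in 20 and four recipients made positive after Day 1.

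| Analysis | All four recipients are true non-responders | One of the four is a true responder |
|---|---|---|
| Truth | 4/20 = 20% | 4/20 = 20% |
| As observed | 8/20 = 40% | 7/20 = 35% |
| Recipients excluded | 4/16 = 25% | 3/16 = 18.8% |
| Recipients as non-responders | 4/20 = 20% | 3/20 = 15% |

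In both cases the truth lies between the as-observed and recipients-as-non-responders results, and exclusion can err either way.

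**The case against.** Much can fairly be said for the plan.

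- **The products are not named.** Section 7.2.2.2 spells out prophylaxis as antibiotics, antifungals and antivirals. Antibody products come in only through the general wording of 7.2.2.1 and the absence of a prohibition; for the solid-tumor cohorts, through silence alone. This stands. It limits how firmly use can be predicted, but it does not supply a rule for handling it.
- **Baseline is taken into account.** GMFR and seroconversion are referred to Day 1, so a participant on steady replacement does not automatically count as a responder. This stands. A reader might infer that the plan systematically overstates response; the documents do not support that, because step 3 shows bias in both directions.
- **Medication is recorded.** Section 7.2.1 requires documentation, Section 6.1.3.1 requires new medications to be recorded at booster Day 1, and later visits review health status or interim history. A reader might infer that booster exposure goes unrecorded altogether; that goes too far. What remains is an unclear window for booster cohorts and none defined for late visits.
- **The deviation criterion could be stretched.** Major deviation is undefined, so the sponsor might try to apply it. As written it does not cover a permitted treatment, and in an open-label trial such a judgement could be made after titers are known.
- **The trial is descriptive.** No hypothesis is tested, the intervals are wide, and the number affected may be zero. This lowers the urgency but does not make an affected estimate interpretable.

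**Conclusion.** The point holds as a gap that should be closed and is cheap to close. Followed exactly, the plan can credit passively acquired antibody to vaccination in the primary bAb and secondary nAb summaries. It has no censoring, flag or sensitivity analysis for this, and recording may not identify exposure before the Day 180, 209, 360 and 394 samples.

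The net direction for GMFR and seroconversion is unknown, since it depends on whether products were on board at Day 1 or came later. The size cannot be derived from the documents. The 5 points per affected non-responder at n = 20 is arithmetic, but the number affected, the passive titers and the 20% true rate are assumptions. It would be tempting to conclude that reported response in the CAR T, CLL or transplant cohorts will be inflated by a stated amount; nothing in the documents supports such an amount, or establishes that any participant will be affected.

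**What to change.** 1. **Recording (7.2.1, Appendices F and G).** Record receipt of antibody-containing products (name and date) at every visit through the last antibody sample in all cohorts, timed from each study injection. Do this first, because exposure not captured during follow-up may not be recoverable.
2. **Flagging (11.4.1.2, 11.4.2.1).** Flag bAb and nAb results drawn within a product-specific interval after receipt, and flag participants with a product on board at Day 1. Fix the intervals before any titer data are reviewed.
3. **Reporting.** Give the number affected per cohort. Present GMT, GMFR and seroconversion as observed and with flagged results excluded. Add seroconversion with post-Day-1 recipients counted as non-responders, because exclusion alone can also raise the rate.

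The cost is one eCRF item per visit, a calendar edit and some extra tables. The excluded-sample analysis will have fewer evaluable results and wider intervals, and it conditions on post-baseline treatment, so it may carry selection of its own; that is why it should not stand alone. Clinical use of these products is unchanged.

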7.2.2.2 Concomitant Medications

Recommendations with regard to specific types of concomitant therapies, supportive care; diet and other interventions are as follows:

- Concomitant medications are recommended as prophylaxis for nausea, vomiting, and infections, and are recommended according to institutional standards. Myelosuppression is expected in participants with acute leukemia, lymphoma or myeloma, or post-stem cell transplantation due to underlying disease, as well as due to chemotherapy, or both. Many participants may have neutropenia, thrombocytopenia, or both at study entry.
- Significant or life-threatening myelosuppression may be managed with growth factor support and blood transfusion according to institutional standard of care, American Society of Clinical Oncology (ASCO) Practice Guidelines, and/or NCCN Practice Guidelines.
- Infections secondary to myelosuppression are common in participants with hematologic malignancies, and may be related to underlying disease, chemotherapy, or both. Therefore, the use of prophylactic antibiotics, antifungal agents, and antiviral agents is recommended according to institutional standards.
- If a prohibited medication is considered essential for the participant well-being, continuation on study with concomitant administration of such medication(s) will need to be discussed with and approved by the principal investigator.

7.3 Laboratory Evaluations

All clinical safety testing will be conducted at CLIA certified laboratories at each site. Blood specimens be obtained in accordance with the study calendar (Appendix C). Blood samples collected for immunology analyses and immune assessments at non-NIH sites will be processed at Moderna Inc. and the NIH using a standardized research operating protocol.

7.3.1 Clinical Laboratory Evaluations

- Urine or serum pregnancy tests will be performed within one week prior to each vaccination on all female participants of childbearing potential. Results must be known prior to each vaccination. (In order to reduce burden on female participants of childbearing potential, the vaccine doses can be prepared and verified, but not administered, while results of the pregnancy test are pending.)

- Clinical laboratory evaluations for safety will be performed by local (clinical) laboratories. Venous blood samples will be collected from each participant prior to each vaccination and according to section **7.3**
- Clinical safety labs include:
 - CBC with differential and platelet count,
 - Chemistry panels including: Acute care panel (Na+, K+, Cl-, total CO2, creatinine, glucose, blood urea nitrogen), and Hepatic panel (AST/GOT, ALT/GPT, total bilirubin, direct bilirubin, alkaline phosphatase)
 - LDH (only collected from participants with CLL)
 - Beta-2 microglobulin (only collected from participants with CLL)

